8.3 Methods of Measurement

The same method of assessment and the same technique should be used to characterize each identified and reported lesion at baseline and during follow-up. Assessments should be identified on a calendar schedule and should not be affected by delays in therapy. While on study, all lesions recorded at baseline should have their actual measurements recorded at each subsequent evaluation, even when very small (e.g. 2 mm). If it is the opinion of the radiologist that the lesion has likely disappeared, the measurement should be recorded as 0 mm. If the lesion is believed to be present and is faintly seen but too small to measure, a default value of 5 mm should be assigned. For lesions which fragment/split add together the longest diameters of the fragmented portions; for lesions which coalesce, measure the maximal longest diameter for the “merged lesion”.

8.3.1 Clinical Lesions

Clinical lesions will only be considered measurable when they are superficial and ≥ 10 mm as assessed using calipers (e.g. skin nodules). For the case of skin lesions, documentation by colour photography including a ruler to estimate the size of the lesion is recommended. If feasible, imaging is preferred.

8.3.2 Chest X-ray

Chest CT is preferred over chest X-ray, particularly when progression is an important endpoint, since CT is more sensitive than X-ray, particularly in identifying new lesions. However, lesions ≥ 20 mm on chest X-ray may be considered measurable if they are clearly defined and surrounded by aerated lung.

8.3.3 CT, MRI

CT is the best currently available and reproducible method to measure lesions selected for response assessment. This guideline has defined measurability of lesions on CT scan based on the assumption that CT slice thickness is 5 mm or less. When CT scans have slice thickness greater than 5 mm, the minimum size for a measurable lesion should be twice the slice thickness. MRI is also acceptable in certain situations (e.g. for body scans). Other specialized imaging or other techniques may also be appropriate for individual case [Eisenhauer 2009]. For example, while PET scans are not considered adequate to measure lesions, PET-CT scans may be used providing that the measures are obtained from the CT scan and the CT scan is of identical diagnostic quality to a diagnostic CT (with IV and oral contrast).

8.3.4 Ultrasound

Ultrasound is not useful in assessment of lesion size and should not be used as a method of measurement. If new lesions are identified by ultrasound in the course of the study, confirmation by CT is advised.

8.3.5 Endoscopy, Laparoscopy

The utilization of these techniques for objective tumour evaluation is not advised. However, they can be useful to confirm complete pathological response when biopsies are obtained or to determine relapse in trials where recurrence following complete response or surgical resection is an endpoint.

8.3.6 *Cytology, Histology*

These techniques can be used to differentiate between PR and CR in rare cases if required by protocol (for example, residual lesions in tumour types such as germ cell tumours, where known residual benign tumours can remain). When effusions are known to be a potential adverse effect of treatment (e.g. with certain taxane compounds or angiogenesis inhibitors), the cytological confirmation of the neoplastic origin of any effusion that appears or worsens during treatment when the measurable tumour has met criteria for response or stable disease is advised to differentiate between response or stable disease and progressive disease.

8.3.7 *Date of Objective Failure (see Section 8.4.6)*

This is defined as the date of the first of the following events, whichever comes first:

- The first record of appearance (radiological or clinical) of local or regional disease progression/recurrence.
- The first record of appearance (radiological or clinical) of distant metastasis.
- Non-protocol RT, chemotherapy, or biologic therapy (for the current OSCC) without documentation of the site of failure.
- Surgery of primary tumour site at any time performed for clinical or radiological (RECIST 1.1) disease persistence/progression/recurrence with tumour present/unknown on final pathology.
- Neck dissection or surgery performed for clinical or radiological (RECIST 1.1) disease persistence/recurrence/progression within the target volumes > 20 weeks from the end of radiation therapy with tumour present/unknown on final pathology.
- Neck dissection or surgery performed for clinical or radiological disease recurrence/progression outside the target volumes or without documentation of the site of failure at any time after registration with tumour present/unknown on final pathology.
- Death due to any cause.

8.3.8 *Date of Progression*

The date of progressive disease is defined as the first day when RECIST (version 1.1) criteria for PD are met. The criteria for PD are met when there is at least a 20% increase in the sum of diameters of measured lesions taking as references the smallest sum of diameters recorded on study (including baseline) AND an absolute increase of $\geq 5\text{mm}$. Appearance of new lesions will also constitute progressive disease (including lesions in previously unassessed areas). In exceptional circumstances, unequivocal progression of non-target disease may be accepted as evidence of disease progression, where the overall tumour burden has increased sufficiently to merit discontinuation of treatment or where the tumour burden appears to have increased by at least 73% in volume. Modest increases in the size of one or more non-target lesions are NOT considered unequivocal progression. If the evidence of PD is equivocal (target or non-target), treatment may continue until the next assessment, but if confirmed, the earlier date must be used.

8.4 Evaluation of Endpoints

As event-free survival is the primary endpoint in this study, it is vital that it be adequately and precisely documented. Due to the difficulties in objectively assessing response following radiation, response will not be a study endpoint but measurements will be recorded to assist with determination of progressive disease and local-regional failure status. Measurements will be taken from CT or MRI and the same method should be used to follow subjects. All subjects will have a clinical and radiological (CT or MRI +/- PET per institutional standards) assessment at 3 months post-completion of RT as defined in Section 5.0.

8.4.1 Local Recurrence or Progression

Local failure will be primarily determined by evidence of progression or recurrence clinically or radiologically. For clinical and radiographic assessments, RECIST 1.1 criteria for progressive or recurrent disease shall be used whenever applicable. In the case of nonmeasurable disease or in circumstances where laryngeal edema complicates the interpretation of radiological measurements, unequivocal clinical description of disease progression or recurrence is required. Biopsy proof (fine needle aspirate is not sufficient) of progressive/recurrent disease is desirable but is not essential if progression/recurrence is documented clinically. Any form of surgery at the primary site will be considered local progression/recurrence unless the pathology shows no evidence of disease.

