Rationale for QOL and resource utilization studies: Recent interest in de-escalation protocols for low-risk HPV-related OPSCC stems from the recognition that: 1) standard treatments result in overtreatment of most patients; and 2) HPV-related OPSCC afflicts generally younger and healthier individuals in the prime of their working years [Marur 2016]. Overtreatment leads to unnecessary toxicity, reduces QOL, increases resource utilization, and results in lost productivity [Machay 2008; Kohler 2013; Yong 2012; Chen 2017; Chera 2015; Ringash 2017; Vainshtein 2015]. OPSCC patients often require increased medical and/or surgical management of osteoradionecrosis, esophageal stricture, trismus, and xerostomia [Aerts 2014; Leijenaar 2015]. Furthermore, ~30% of patients require emergency care during treatment, and ~40% report a change in work status after treatment [Kohler 2013]. The impact of overtreatment on QOL has been reported to differ between HPV-related and HPV-unrelated OPSCC [Gross 2014]. The long-term impact of OPSCC treatment on QOL is thought to stabilize by 2 years post-treatment [Bratman 2016], suggesting that this duration of follow up is sufficient for prospective studies.

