8.0 CRITERIA FOR MEASUREMENT OF STUDY ENDPOINTS

8.1 Definitions

8.1.1 *Evaluable for Adverse Events*

All patients will be evaluable for adverse event evaluation from the time of their first treatment.

8.1.2 *Evaluable for Quality of Life Assessment*

All patients who have completed the quality of life questionnaire are evaluable for quality of life.

8.1.3 *Evaluable for Health Economics Assessment*

All enrolled patients are evaluable for health economics. Those who have completed the resource utilization and lost productivity questionnaires will be evaluable for cost-utility analyses.

8.1.4 *Evaluable for Event-free Survival*

Event-free survival (EFS) is defined as the time from the date of registration to the date of first record of any of the following events:

- Investigator determined:
 - Local-regional progression or recurrence.
 - Distant metastasis.
- Surgery:
 - Surgery at any time for clinical or radiological (RECIST 1.1) disease persistence/progression/recurrence at the primary tumour site with tumour present/unknown on final pathology.
 - Neck dissection or surgery performed for clinical or radiological (RECIST 1.1) disease persistence/recurrence/progression within the target volumes > 20 weeks from the end of radiation therapy with tumour present/unknown on final pathology.
 - Neck dissection or surgery performed for clinical or radiological disease recurrence/progression outside the target volumes or without documentation of the site of failure at any time after registration with tumour present/unknown on final pathology.
- Non-protocol RT, chemotherapy, or biologic therapy (for the current cancer diagnosis) without documentation of the site of failure.
- Death due to any cause.

8.1.5 *Local-regional Control (LRC)*

Local-regional control is defined as the time from the date of registration to the date of any of the following, whichever comes first:

- Surgery of primary tumour at any time performed for clinical or radiological (RECIST 1.1) disease persistence/progression/recurrence with tumour present/unknown on final pathology

- Neck dissection > 20 weeks from the end of radiation therapy performed for clinical or radiological (RECIST 1.1) disease persistence/progression/recurrence within target volumes with tumour present/unknown on final pathology

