8.4.3 Out-of-field Regional Failure

An out-of-field regional failure is defined as regional recurrence or progression outside the treatment field. Subjects with clinical or radiological evidence concerning for nodal failure outside the treatment field should have pathologic confirmation and restaging for local and distant disease. A positive biopsy and/or a neck dissection at any time after registration performed for suspected nodal failure outside the treatment field that is positive/unknown for tumour on pathology will be considered out-of-field regional failure. Subjects who do not have a neck dissection because their neck disease is judged to be unresectable will only be deemed to have failure in the neck after biopsy or cytological confirmation is obtained or disease progression is documented.

If failure is not confirmed, subjects may be observed with CT repeated at 3 monthly intervals or following local institutional guidelines to confirm stability or regression of the lymph nodes.

Categorizing regional failure as in-field or out-of-field will be done by the local investigator based on review of the original treatment volumes and the site of tumour recurrence in the neck. Post-hoc central review of the patterns of regional failure will also be performed on all subjects that have regional failure (either as first or subsequent recurrence).

8.4.4 *Local-regional Failure*

This is defined as local failure, regional failure or both. For the purposes of determining site of first failure the category of both will be applicable if local and regional failure occurs within one month of each other.

8.4.5 *Distant Metastasis*

This is defined as the presence of positive pathological or radiological evidence of recurrent disease at any site of the body with the exception of those defined as 'local' or 'regional'.

When distant metastases are the first indication of relapse, then the patient must be examined for local-regional disease.

8.4.6 *Event-Free Survival Endpoint*

First Event	Event-free Survival
None	Censored
Local-regional progression or recurrence	Failure
Distant metastasis	Failure
Non-protocol RT, chemotherapy, or biologic therapy (for the current OPSCC) without documentation of the site of failure	Failure
Surgery of primary site (at any time after RT) with tumour present/unknown	Failure
Neck dissection with tumour present/unknown, > 20 weeks from end of RT	Failure

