Neck dissection (at any time after registration) with tumour present/unknown outside the treatment field	Failure
Death due to study cancer or from unknown causes	Failure
Death due to any other reason	Failure

Note: The following are not considered events:

- Second primary neoplasm which is defined as a primary head and neck tumour which does not fulfill the criteria for local progression/recurrence or a neoplasm arising from a non-head and neck site;
- Surgery of primary with no tumour on pathology specimen;
- Planned neck dissection for disease inside the treatment field \leq 20 weeks from end of RT;
- Neck dissection with no tumour on pathology specimen.

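### Protocol 8.4.1 and the 8.4.6 surgery row omit the disease indication that 8.1.4 and the SAP require, so primary-site surgery for a complication without clear pathology can count as an EFS event

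*Protocol*

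**What the plan says.** The documents contain two rules for surgery at the primary site.

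**Rule with an indication.** Protocol 8.1.4 counts as an EFS event "Surgery at any time for clinical or radiological (RECIST 1.1) disease persistence/progression/recurrence at the primary tumour site with tumour present/unknown on final pathology". SAP 2.5.1 repeats this item. Protocol 8.3.7 (date of objective failure) has "Surgery of primary tumour site at any time performed for clinical or radiological (RECIST 1.1) disease persistence/progression/recurrence with tumour present/unknown on final pathology". The LRC definitions in protocol 8.1.5 and SAP 2.5.3 carry the same limit. Two conditions must both hold: the surgery was for disease, and tumour was present or unknown.

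**Rule without an indication.** The last sentence of protocol 8.4.1 reads "Any form of surgery at the primary site will be considered local progression/recurrence unless the pathology shows no evidence of disease". The EFS table in protocol 8.4.6 lists as a failure "Surgery of primary site (at any time after RT) with tumour present/unknown". The note under that table exempts "Surgery of primary with no tumour on pathology specimen" and has no exemption for surgery done for a treatment complication.

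The heading of 8.3.7 refers the reader to 8.4.6, although the two differ on this point. No passage says which section governs.

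**The concern.** Section 8.4.1 is where an investigator looks to decide what local progression is. Local-regional progression or recurrence, as determined by the investigator, is a separate EFS event in protocol 8.1.4 and SAP 2.5.1. Its first record is also an LRC event in protocol 8.1.5 and SAP 2.5.3. The 8.4.1 sentence can therefore feed the primary endpoint without the surgery item ever being met. For example, a procedure to control bleeding at the primary site that yields no specimen has not been shown to be free of disease, so 8.4.1 read literally makes it local progression.

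At stake is a late toxicity recorded as a cancer failure in a de-escalation trial that evaluates late toxicity separately. The origin of such an event could also be hard to see afterwards. SAP 2.5.1 ranks progression above surgery for simultaneous events, so SAP Table 6 could list it as progression.

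**Working it through.** **Step 1: where the rules differ.**

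| Primary-site surgery | 8.1.4 / SAP 2.5.1 surgery item | 8.4.1 sentence and 8.4.6 row |
|---|---|---|
| For disease, tumour present or unknown | Event | Event |
| For disease, no tumour | No event | No event |
| For a complication, no tumour | No event | No event |
| For a complication, tumour found | Not under this item, but normally a recurrence anyway | Event |
| For a complication, pathology absent or unknown | No event | Event |

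In practice the conflict is confined to the last line.

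**Step 2: reproduce the decision rule.** The inputs, from protocol 13.3 and SAP 1.2, are 2-year EFS of 85% (H0) and 91% (Ha), 304.7 person-years, one-sided alpha 0.1, and rejection of H0 at 18 or fewer events (observed rate 88.85% or higher). I assume a constant hazard and a Poisson event count.

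- Hazard under H0: −ln(0.85)/2 = 0.08126 per year; × 304.7 = 24.76 expected events.
- Hazard under Ha: −ln(0.91)/2 = 0.04716 per year; × 304.7 = 14.37 expected events.
- P(18 or fewer | H0) = 0.0999 and P(19 or fewer | H0) = 0.1438, so 18 is the largest cut-off that keeps alpha within 0.10.
- Observed rate at 18 events: exp(−2 × 18/304.7) = 88.86%, matching the stated 88.85% apart from the last digit. At 19 events: exp(−2 × 19/304.7) = 88.28%.
- P(18 or fewer | Ha) = 86.1% ignoring the interim analysis. With the futility stop at 12 or more events in 162.9 person-years (protocol 13.5) it is 82.9%.

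The cut-off and the alpha bound reproduce. Power meets the stated 80%.

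**Step 3: the margin is one event.** P(exactly 18 | Ha) = P(18 or fewer) − P(17 or fewer) = 0.861 − 0.800 = 0.061. In a trial with exactly 18 correctly classified events, one further event counted by the 8.4.1 route changes rejection of H0 into non-rejection. This needs no assumption about how often such procedures occur.

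**Step 4: illustration.** The documents give no rate of complication surgery at the primary site with unknown pathology. Assume that 0.5%, 1% or 2% of 100 patients have one, that each is counted, and that none of these patients would otherwise have had an event. Add 0.5, 1 or 2 to the expected count:

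| Extra expected events | Mean under Ha | P(18 or fewer given Ha) | P(18 or fewer given H0) |
|---|---|---|---|
| 0 | 14.37 | 86.1% | 0.100 |
| 0.5 | 14.87 | 82.9% | 0.084 |
| 1 | 15.37 | 79.3% | 0.070 |
| 2 | 16.37 | 71.1% | 0.049 |

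These figures ignore the interim analysis. The 82.9% in the 0.5 row equals the 82.9% futility-stop baseline of step 2 only by coincidence. The H0 column falls as well, so type I error is not inflated.

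**The case against.** The strongest reply is that the analysis definition already settles the matter. SAP 2.5.1 and 2.5.3 state the indication, and protocol 8.1.4, 8.1.5 and 8.3.7 agree with them. The 8.4.6 table reads as shorthand: its neck-dissection rows drop the indication too. Section 8.4.1 itself opens by resting local failure mainly on clinical or radiological evidence, so its last sentence bites only if it is taken literally against that opening. Operative and pathology reports are mandatory uploads with the relapse/progression report (Appendix III), and central data review confirms endpoints (protocol 11.1).

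Much of this stands. The conflict rests mainly on one sentence, and affected cases should be few. It does not remove the problem. The investigator-determined progression item bypasses the surgery item, 8.4.1 tells the investigator what counts, and a central reviewer would still face two definitions.

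Two stronger readings are not supported:

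- **Frequency.** A reader might infer from the background statement "OPSCC patients often require increased medical and/or surgical management of osteoradionecrosis, esophageal stricture, trismus, and xerostomia" that such events will be common. That sentence does not place the surgery at the primary site and gives no rate there.
- **An opposite-direction gap for neck dissection.** Section 8.1.4 counts tumour-positive or unknown neck surgery "outside the target volumes or without documentation of the site of failure at any time after registration", while the any-time row of 8.4.6 has only "Neck dissection (at any time after registration) with tumour present/unknown outside the treatment field". A reader might infer that a dissection at 20 weeks or earlier with undocumented site escapes the endpoint. It does not. Section 8.4.2, on regional recurrence or progression, calls that case a treatment failure, and 8.4.6 has a general row for local-regional progression or recurrence. The any-time row is merely abbreviated.

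**Conclusion.** The inconsistency is real and sits in the primary endpoint, but it is narrow. It concerns primary-site surgery for a complication with absent or unknown pathology. It runs against the treatment: it can lower power and push towards a false negative, and it cannot make a false positive more likely.

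The firm part of its size is the one-event margin between 18 and 19. The falls to 82.9%, 79.3% and 71.1% are hypothetical. They rest on assumed procedure rates, a constant hazard, and every such procedure being counted in a patient with no other event. The documents do not support a claim that the trial's result is likely to be changed. The point is worth correcting because the remedy costs almost nothing.

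**What to change.** 1. State that protocol 8.1.4 and SAP 2.5.1 are the governing EFS definition.
2. Add the disease-indication condition already used in 8.1.4 to the last sentence of 8.4.1 and to the primary-surgery row of 8.4.6.
3. State that, for the endpoint, surgery for a treatment complication counts only if its specimen shows tumour. This settles the case of no specimen or unknown pathology.
4. Enrolment is complete (103 patients, SAP 1.6), so apply this as a documented adjudication rule, with a targeted query on the indication for every primary-site surgery, before the analysis. LRC should follow the same rule.
5. Optional tidying: add the undocumented-site case to the any-time neck-dissection row of 8.4.6. This changes no event.

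The cost is two wording edits, a short adjudication note and a limited data query. Operative and pathology reports are already collected for cases reported as relapse. Primary-site surgeries not reported as relapse would need the query. Sample size, cut-off and analysis method do not change.

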8.4.2 Regional Lymph Node Recurrence or Progression

Neck dissection performed for clinical or radiological (RECIST 1.1) disease persistence/progression/recurrence within target volumes after 20 weeks from the end of radiation therapy with evidence of tumour present or unknown will be considered a treatment failure.

Neck dissection performed at any time after registration for clinical or radiological (RECIST 1.1) disease recurrence/progression outside the target volumes or without documentation of the site of failure with tumour present/unknown will be considered a treatment failure.

Development of any new clinically or biopsy proven malignant regional nodes not present at baseline or clinically or biopsy proven recurring or progressing nodes will be considered evidence of regional recurrence/progression.

8.4.3 Out-of-field Regional Failure

An out-of-field regional failure is defined as regional recurrence or progression outside the treatment field. Subjects with clinical or radiological evidence concerning for nodal failure outside the treatment field should have pathologic confirmation and restaging for local and distant disease. A positive biopsy and/or a neck dissection at any time after registration performed for suspected nodal failure outside the treatment field that is positive/unknown for tumour on pathology will be considered out-of-field regional failure. Subjects who do not have a neck dissection because their neck disease is judged to be unresectable will only be deemed to have failure in the neck after biopsy or cytological confirmation is obtained or disease progression is documented.

If failure is not confirmed, subjects may be observed with CT repeated at 3 monthly intervals or following local institutional guidelines to confirm stability or regression of the lymph nodes.

Categorizing regional failure as in-field or out-of-field will be done by the local investigator based on review of the original treatment volumes and the site of tumour recurrence in the neck. Post-hoc central review of the patterns of regional failure will also be performed on all subjects that have regional failure (either as first or subsequent recurrence).

8.4.4 *Local-regional Failure*

This is defined as local failure, regional failure or both. For the purposes of determining site of first failure the category of both will be applicable if local and regional failure occurs within one month of each other.

8.4.5 *Distant Metastasis*

This is defined as the presence of positive pathological or radiological evidence of recurrent disease at any site of the body with the exception of those defined as 'local' or 'regional'.

When distant metastases are the first indication of relapse, then the patient must be examined for local-regional disease.

8.4.6 *Event-Free Survival Endpoint*

First Event	Event-free Survival
None	Censored
Local-regional progression or recurrence	Failure
Distant metastasis	Failure
Non-protocol RT, chemotherapy, or biologic therapy (for the current OPSCC) without documentation of the site of failure	Failure
Surgery of primary site (at any time after RT) with tumour present/unknown	Failure
Neck dissection with tumour present/unknown, > 20 weeks from end of RT	Failure
Neck dissection (at any time after registration) with tumour present/unknown outside the treatment field	Failure
Death due to study cancer or from unknown causes	Failure
Death due to any other reason	Failure

Note: The following are not considered events:

- Second primary neoplasm which is defined as a primary head and neck tumour which does not fulfill the criteria for local progression/recurrence or a neoplasm arising from a non-head and neck site;
- Surgery of primary with no tumour on pathology specimen;
- Planned neck dissection for disease inside the treatment field \leq 20 weeks from end of RT;
- Neck dissection with no tumour on pathology specimen.

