7.2.18 Central Review of Regional Failures

With reduction of the elective nodal irradiation volumes, there may be increased risk of out-of-field regional recurrence. Rigorous analysis of patterns of failure in the neck will be important for informing the results of this study and any future studies that utilize a similar treatment approach.

Any subject with regional recurrence in the lymph nodes of the neck (either as first or subsequent recurrence) will require central review of the radiological images (CT, MRI, and/or PET-CT) obtained at the time of recurrence in order to categorize the regional recurrence as in-field or out-of-field. The radiological images showing regional recurrence will be submitted within 4 weeks of confirming the recurrence.

The recurrent tumour volume will be identified on the earliest available diagnostic scan that shows the recurrent node. If the identified recurrent lymph node corresponds to a lymph node that was present on the planning scan, the node from the planning scan will be contoured and named “RECUR_NODE.” Otherwise, the identified recurrent lymph node volume will be contoured on the radiological images obtained at the time of recurrence and named “RECUR_NODE”; following registration to the planning scan, the RECUR_NODE volume will be transferred to the planning CT structure set.

The radiation dose received by the RECUR_NODE volume will be determined.

An “in-field regional recurrence” will be defined in cases in which $\geq 95\%$ of RECUR_NODE was within the 95% isodose of PTV_5600.

An “out-of-field regional recurrence” will be defined in cases in which $< 95\%$ of RECUR_NODE was within the 95% isodose of PTV_5600.

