11.2 Central Radiology Review

For any patient with local-regional failure, central radiology review will be performed to confirm site of failure. Please refer to Section 7.2.18.

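### In-field versus out-of-field regional failure has two deciders and two tests, and the SAP does not say which label is analysed for out-of-field regional control

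*Protocol*

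**What the plan says.** **Local call.** Protocol 8.4.3: "Categorizing regional failure as in-field or out-of-field will be done by the local investigator based on review of the original treatment volumes". Where the tumour recurred in the neck is considered as well. No dose or overlap threshold is given. The same paragraph adds: "Post-hoc central review of the patterns of regional failure will also be performed on all subjects that have regional failure".

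**Central call.** Protocol 7.2.18 requires central image review "in order to categorize the regional recurrence as in-field or out-of-field". A recurrence is in-field when at least 95% "of RECUR_NODE was within the 95% isodose of PTV_5600", and out-of-field otherwise. The trigger is: "Any subject with regional recurrence in the lymph nodes of the neck (either as first or subsequent recurrence) will require central review". Protocol 11.2 adds: "For any patient with local-regional failure, central radiology review will be performed to confirm site of failure".

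**Boundary terms.** Protocol 8.1.6, which defines the out-of-field endpoint, uses *treatment field* for a recurrence and *target volumes* for a neck dissection. Protocol 8.1.4 counts as an EFS event a tumour-positive or tumour-unknown dissection for "recurrence/progression outside the target volumes or without documentation of the site of failure at any time after registration". Protocol 8.4.6 lists as a non-event "Planned neck dissection for disease inside the treatment field" up to 20 weeks after radiotherapy, with no condition on pathology. Neither term is tied to the 7.2.18 rule.

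**SAP.** Section 2.5.4 refers only to the treatment field, omits the dissection component of Protocol 8.1.6, and does not say whose classification is used. Table 9 lists a neck dissection *within* target volumes as a type of out-of-field event.

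**The concern.** For out-of-field regional control, the label is the endpoint. Protocol 7.2.18 itself says that reduced elective volumes may raise the risk of out-of-field recurrence and that rigorous failure analysis is important. If the two tests disagree on a case, the plan gives no rule for resolving it. In an open single-arm trial, leaving that choice until the cases are known invites doubt about the result.

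There is also a gap in the check. Every mandatory trigger for central review needs a regional recurrence or failure. An early dissection that the site regards as in-field persistence is neither, so a mistaken call in that direction has no mandatory second look.

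**Working it through.** The plan states no figure for this classification, so the provisions are compared first. The EFS rule is then reproduced to show what a miscalled case would act on.

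**1. Two tests on one recurrence.** The elective dose is 56 Gy (Protocol 7.2), so the 95% isodose is 0.95 × 56 = 53.2 Gy.
- *Omitted level, incidental dose.* If at least 95% of the node lies within 53.2 Gy, 7.2.18 calls it in-field, yet it lies outside the target volumes named in 8.1.6.
- *Node across the edge.* 7.2.18 has a 95% cut-off and 8.4.3 has none. Assume a spherical node with r = 10 mm that overhangs a flat isodose edge by h. The fraction outside is h²(3r − h)/(4r³).
  - h = 2 mm: 4 × 28/4000 = 2.8%, in-field.
  - h = 3 mm: 9 × 27/4000 = 6.1%, out-of-field.

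The second calculation shows how sharp the dose rule is. It does not estimate how often site and centre would disagree.

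**2. Effect on the secondary endpoint.** Called out-of-field, the case is an event under 8.1.6. Called in-field, it is not. In-field regional failure is also not among the competing events listed there, so on the wording the patient simply stays at risk.

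**3. Dissection at 20 weeks or earlier, tumour present or unknown.**

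| Site's description | EFS | Mandatory central review |
|---|---|---|
| New malignant, recurring or progressing node, any location | Failure (8.4.2, 8.1.4) | Yes |
| Recurrence or progression outside target volumes, or site undocumented | Failure (8.1.4) | Yes |
| Persistent disease inside the field | Not an event (8.4.6) | None under 7.2.18, 8.4.3 or 11.2 |

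After 20 weeks, a dissection with tumour present or unknown is a failure under either label. The EFS exposure is therefore a case that belongs in one of the first two rows but is recorded in the third.

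**4. What one such case would act on.** Inputs from Protocol 13.3: 2-year EFS 85% (H0) and 91% (Ha), 304.7 person-years, limit 18 events, one-sided alpha 0.1, power 80%. The model is exponential EFS with a Poisson event count.
- Hazards: −ln(0.85)/2 = 0.08126 and −ln(0.91)/2 = 0.04716 per year.
- Expected events: 24.76 (H0) and 14.37 (Ha).
- P(X ≤ 18 | H0) = 0.0999, and exp(−2 × 18/304.7) = 88.86% against the stated 88.85%. The rule reproduces.
- P(X ≤ 18 | Ha) = 0.861, or 0.829 with the interim stop, against the stated 80%.

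Now **assume** that k true events are always left uncounted, so that the rule passes up to 18 + k. In the other direction, assume k non-events are counted. The interim stop is ignored; including it gives alpha 0.089 at k = 0.

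| k | Alpha if k events are missed | Power if k are wrongly added |
|---|---|---|
| 0 | 0.0999 | 0.861 |
| 1 | 0.144 | 0.800 |
| 2 | 0.198 | 0.723 |
| 3 | 0.262 | 0.633 |

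No value of k comes from the documents.

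**The case against.** **EFS is largely protected.** Protocol 8.4.2 makes any new malignant, recurring or progressing node a regional failure with no field condition. A node appearing in an omitted level is normally new, so it counts for EFS and reaches review under either label. This stands. A reader might infer that the field label drives the primary endpoint broadly, or that central review misses the cases most in need of it. The text supports neither.

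**Early in-field dissections concern treated nodes.** Protocol 7.3.1 deals with residual treated nodes. Gross nodes receive a 5 mm CTV margin plus a 3–5 mm PTV margin, so 8–10 mm before trimming (7.2.8). Contours and diagnostic imaging are approved centrally before treatment (7.2.17). For these nodes the label should seldom be in doubt. This also stands, and it makes the gap small. It does not close it, because the split between persistence and progression is itself a site judgement.

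**Other checks exist.** Protocol 11.1 provides central source review of endpoints, which can include surgical and pathology reports. That could surface a case, but it does not require the dose review.

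**The dose rule has faults.** It can call an omitted-level recurrence in-field because of incidental dose, which removes it from the endpoint meant to test omission. This is fair, and it is why the local call should be listed and analysed alongside.

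**Investigator-determined progression is a stated choice.** Both Protocol 8.1.4 and SAP 2.5.1 say so. Imposing the central dose rule on primary EFS would be a redesign, and the inconsistency does not justify it.

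**Conclusion.** This is a cheap improvement. The protocol classifies the same recurrence by two tests applied by two deciders, and neither document says which result is analysed for out-of-field regional control. Each disputed case moves that secondary endpoint by one event. The documents give neither an expected number of out-of-field failures nor a disagreement rate, so no overall size can be stated.

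The review gap is real but narrow. It is confined to tumour-positive or tumour-unknown dissections at 20 weeks or earlier that the site calls in-field persistence. It affects EFS only when a new, progressing or out-of-field node is miscalled that way. A reader might take alpha of 0.144 to 0.262 as the trial's actual type I error. It is not: those values assume 1 to 3 missed events, whereas correctly labelled early in-field dissections are non-events by design. They show only that the 18-event limit has almost no slack.

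**What to change.** - **Out-of-field regional control (Protocol 8.1.6, 8.4.3; SAP 2.5.4).** State that the central 7.2.18 classification is analysed. List the local call beside it and report a sensitivity analysis under the local call.
- **Terms.** Reconcile *target volumes* and *treatment field* across 8.1.4, 8.1.6 and 8.4.6. Align SAP 2.5.4 and Table 9 with Protocol 8.1.6, including the dissection component.
- **Central review.** Extend 7.2.18 to every neck dissection with tumour present or unknown, including those at 20 weeks or earlier.
- **EFS.** Keep the primary analysis investigator-determined. Add a sensitivity analysis using the central label for dissection events.

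**Cost.** Wording, plus a few extra cases in a review that already exists. Every patient's plan already goes through central review (7.2.17), and Section 5.0 already schedules head and neck imaging at 3 and 6 months. Some secondary-endpoint calls will wait for the central result. Sample size and patient management do not change.
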